Interleukin-1 Blockade in Recently Decompensated Heart Failure

A Randomized Placebo-controlled Double-blinded Study

The REDHART2 study

STUDY PROTOCOL

Principal Investigators:
[name], PhD;
[name] [name]

Virginia Commonwealth University

CHANGES TO PRIOR VERSION

Prior version dated 10-25-2018 → new version 11-13-2018

- Personnel updated in the DSMB Charter per NHLBI Liaison request (see also section 8.6, and DSMB charter);
- Modified BNP criteria to include also NT-proBNP criteria – according to the European Society of Cardiology 2016 Heart Failure Guidelines (Ponikowski P et al. Eur Heart J 2016;37:2129-2200.

Prior version dated 11-13-2018 → new version 01-23-2019

- **Section 5.2:** Addition of the IPAQ questionnaire to the quality of life assessments. It will be administered at baseline, 6, 12 and 24 weeks to assess patient perception of changes
- **Section 6.3:** Changed exclusion criteria from “prior or current malignancy” to just “current malignancy receiving targeted therapy”.
- **Section 7.1:** We clarify that the patient may need to come for additional visits between the pre-specified clinic visits for assessment and/or drug dispensing.
- **Section 7.7:** Addition of the IPAQ questionnaire to the list of study activities and clarification on when a physician will be alerted to review a participant’s chart based on questionnaire responses.
- **Section 11.3.2:** Clarification on when cases with missing CPX data will result in omission from efficacy analysis.

DSMB Charter 3.f.: Clarification of the Biostatistician as Voting Member of the DSMB.

Prior version dated 01-23-2018 → new version 03-14-2019

- **Section 5.2:** Updated echocardiography description to include 6 and 12 week ECHO timepoints
- **Sections 7.5 and 7.9:** Updated echocardiography paragraph and procedure table to include ECHOs at weeks 6 and 12
- **Section 7.8:** Removed “troponin I” from text as biomarker being tested

Prior version dated 03-14-2019 → 08-27-2019

- Section 6.3: Clarified exclusion criterion related to CRT and valve surgery ('Cardiac resynchronization therapy (CRT) during index hospitalization, or planned CRT or valve surgeries within the following 6 months').
- Section 7.9: Corrected the time window for Visit 4 to 168 ± 14 days (24 ± 2 weeks).
- Section 8.3.1: We have updated the AE section to list the most common risks related to anakinra or completion of the study procedures.
- Section 10.1: We clarified that arthritis is a manifestation of hypersensitivity reaction that can demand discontinuation of the drug.

Prior version dated 08-27-2019 → 10-07-2019

- Section 10.1: Specified the rules for restarting study drug after it has been suspended
- Section 10.2: Distinction between withdrawing treatment and withdrawing from the study and clarification of how long each patient will be followed for safety reasons and how the data will be used after each type of withdrawal
- Section 11.3.2: Clarification of primary method for handling missing data (LOCF)

Temporary Amendment in response to COVID19 Pandemic Emergency 03/27/2020

- Enrollment has been halted on 03/17/2020.
- All patients were instructed to interrupt treatment on that date.
- Follow up provided to assess for any research-related adverse events up to 6 months.
- Adjudication for events after 03/17/2020 will not be completed in consideration of the dynamic changes in the clinical care, challenges in diagnosis ascertainment, and possibility of COVID19 contributing to excess cardiovascular events.

Resuming clinical research operations during COVID19 pandemic change in Protocol version dated 10-07-2019 → 04-24-2020

- Resume screening and enrollment when Governor of Virginia and VCU / VCU Health authorize resumption of elective clinical procedures.
- Change in exclusion criteria, adding a criterion related to COVID19:
 - Evidence of COVID19 within the last 60 days or recent (21 days) exposure to close personal contact. (Section 6.3, bullet 9).

Changes to Key Personnel and DSMB Charter

- [name], has taken on a new position as Associate Director of the Pauley Heart Center and will no longer serve as Regulatory Coordinator for the REDHART2 study; [name] will however serve as DSMB Liaison to the study instead of [name], who has left VCU as June 10, 2020.

- 1) Key Personnel**
- 2) Protocol summary**
- 3) Schematic of study design**
- 4) Description**
- 5) Objectives**
 - 5.1 Primary Endpoint(s)
 - 5.2 Secondary Endpoints
- 6) Enrollment in the study**
 - 6.1 Screening
 - 6.2 Inclusion criteria
 - 6.3 Exclusion criteria
 - 6.4 Alternate consent
- 7) Study design**
 - 7.1 Clinical assessment
 - 7.2 Randomization and allocation concealment
 - 7.3 Investigational treatment
 - 7.4 Cardiopulmonary exercise test
 - 7.5 Echocardiogram
 - 7.6 Non-invasive hemodynamics and bio-impedance
 - 7.7 Questionnaires
 - 7.8 Biomarkers
 - 7.9 Study Schedule
 - 7.14 Cost coverage analysis

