9.2 Definition of the events

The events adjudicated will include:

- Death;
- Cardiac death (in which a direct cause attributable to cardiac disease is present);
- Sudden cardiac death (in which cardiac death occurred out of the hospital and suddenly; or in the hospital due to ventricular arrhythmias unrelated to other concomitant cardiac conditions);
- Non-cardiac death (in which the event of death is considered not to be a direct consequence of cardiac disease);
- Hospitalization for any cause;
- Hospitalization for heart failure (in which the primary diagnosis for hospitalization is decompensated heart failure established as the finding at admission of all 2 conditions listed: *a.* dyspnea or respiratory distress or tachypnea at rest or with minimal exertion; *b.* evidence of elevated cardiac filling pressure or pulmonary congestion (at least one of the conditions must be met: pulmonary congestion/edema at physical exam OR chest X-ray; plasma BNP levels ≥ 200 pg/ml; or invasive measurement of left ventricular end-diastolic pressure > 18 mmHg or of pulmonary artery occluding pressure (wedge) > 16 mmHg);
- Outpatient worsening of heart failure (defined as the need for intravenous diuretic treatment or need for increase in oral diuretic dose, or new prescription for first or add-on diuretic);
- Acute myocardial infarction, as defined by the WHO consensus statement 4th edition;
- Unstable angina, or need for coronary revascularization;

- Cardiac tachy-or brady-arrhythmias leading to a new hospitalization or to prolongation of hospital stay;
- Acute renal failure (defined as an increase in plasma creatinine levels of 50% or 0.5 mg/L);
- Acute respiratory failure (not due to heart failure);
- Sepsis or other serious infection requiring antibiotic therapy;
- Acute stroke.

The analysis will consider time to first event and time to each event. It will also consider event rates at 1, 3 and 6 months, in order to favor comparisons with other studies. The number of days free of hospitalization during the first 1, 3 and 6 months will also be measured and compared between groups.

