11.2 Sample Size Considerations

The sample size for this pilot study is calculated according to the primary endpoint of

difference in interval change in peak VO_2 at 24 weeks between anakinra and placebo. Given an expected average peak VO_2 of 15 mL/kg/min for HF patients, 68 subjects randomized to anakinra and 34 subjects randomized to placebo (2:1 randomization) would provide approximately >95% power to detect a difference of 1.6 $\text{mL}\cdot\text{kg}^{-1}\cdot\text{min}^{-1}$ (standard deviation of 1.7-2.0 $\text{mL}\cdot\text{kg}^{-1}\cdot\text{min}^{-1}$) in peak VO_2 on top of placebo. A conservative estimate of 20% loss to follow-up or withdrawal would retain >90% power.

		Effect size of treatment on top of placebo				
	$\text{mL}\cdot\text{kg}^{-1}\cdot\text{min}^{-1}$	+1.2	+1.4	+1.6	+2.4	+3.2
Standard Deviation	2.3	0.70	0.83	0.91	>0.99	>0.99
	2.0	0.82	0.92	0.97†	>0.99	>0.99
	1.7	0.92	0.98	0.99	>0.99	>0.99
	1.4	0.98	0.99	>0.99	>0.99	>0.99*

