11.3 Statistical Analysis

11.3.1 Demographics and Baseline Characteristics

Descriptive summaries of continuous measurements will be reported as median and interquartile ranges due to potential deviation from Gaussian distribution. Descriptive summaries of categorical measurements consist of frequencies, proportions and 95% confidence intervals, when applicable. All analyses will be conducted after database locking once all data has been gathered and electronically captured. All analyses will be based on the intention-to-treat principle (i.e., analyzing groups as randomized and including all patients with outcome data available). The difference in interval changes in peak VO_2 at 24 weeks between the anakinra vs. placebo groups will be compared using random-effect analysis of variance for repeated measures to analyze the effects of treatment within each group and the effect of time_x_group allocation. Unadjusted p-values will be reported throughout, with statistical significance for the primary endpoint set at the 2-tailed 0.050 level. To evaluate the group differences in the secondary endpoints, data will be compared across all groups using the random-effect analysis of variance for repeated measures as indicated above for paired analyses, or Kaplan-Meier curves with Log-rank testing for event rates.

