11.3.2 Handling of Missing Data

Cases with missing data for all follow-up CPX at 6, 12 and 24 weeks will be omitted from the efficacy analysis due to inability to calculate the primary endpoint (change in peak VO_2). Considering that the main variable of interest (peak VO_2) is expected not to improve over time with placebo in patients with systolic HF and exclusion of patient with missing

data would inevitably lead to a survivorship bias, we will use the last observation carried forward (LOCF) method to impute the missing data at 12 and 24 weeks for the primary analysis. We will also perform the Little's Missing Completely At Random (MCAR) test to determine whether the appropriateness of imputing missing values and perform a Multivariate Imputation by Chained Equation (MICE) to validate the finding of peak VO₂ using a different method for data inference.

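### The analysis sections have no rule for patients whose drug was stopped on 17 March 2020: 6-month event summaries run past the end of adjudication, and LOCF can put an early value in place of the 24-week endpoint

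*Combined protocol and SAP*

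**What the plan says.** The change history at the front of the protocol contains a temporary amendment dated 27 March 2020. It reports that enrollment stopped on 17 March 2020 and that "All patients were instructed to interrupt treatment on that date". Follow-up for research-related adverse events continued for up to 6 months. On events it states "Adjudication for events after 03/17/2020 will not be completed in consideration of the dynamic changes in the clinical care", with no end date. The next entry (24 April 2020) covers only the resumption of screening and enrollment and a new exclusion criterion.

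The analysis text does not mention the halt:

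- Section 9.2 plans time-to-event analyses and adds "It will also consider event rates at 1, 3 and 6 months", with hospitalization-free days over the same windows.
- Section 11.3.1 names Kaplan-Meier curves and the log-rank test, without a censoring rule. It analyses patients as randomized where outcome data exist.
- Section 11.3.2 says of missing 12- and 24-week peak VO₂ that "we will use the last observation carried forward (LOCF) method" for the primary analysis. It omits patients with no follow-up exercise test and plans multiple imputation as a check.
- Section 11.3.3 says that all analyses are complete case.

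**The concern.** A difference between a change log and the current text is not in itself an error. This entry, however, does not describe superseded wording. It records what happened to patients and to the data, and no later entry reverses it.

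Two things are at stake. First, a 6-month adjudicated event rate needs 6 months of adjudication. For a patient on study at the halt, part of that window can contain no adjudicated event. If such patients stay in the denominator, the rate is too low and the hospitalization-free days may be too high.

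Second, section 11.3.2 justifies LOCF by the survivorship bias that would follow from dropping patients with missing data. A stop ordered on a calendar date is unrelated to a patient's course, so that reason does not apply. LOCF would still report a 6- or 12-week on-treatment value as the 24-week result. The protocol's own account of the pilot suggests that duration matters: 12 weeks of anakinra improved peak VO₂ and 2 weeks did not.

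**Working it through.** **1. The plan's power figure.** Inputs from sections 11.2 and 11.3.1: "68 subjects randomized to anakinra and 34 subjects randomized to placebo (2:1 randomization"), "power to detect a difference of 1.6" mL/kg/min, "standard deviation of 1.7-2.0", and "statistical significance for the primary endpoint set at the 2-tailed 0.050 level".

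- Standard error at SD 2.0: 2.0 × √(1/68 + 1/34) = 0.420.
- Ratio: 1.6/0.420 = 3.81. Power = Φ(3.81 − 1.96) = 0.968, or 0.965 with the noncentral t. The plan's table gives 0.97, so it reproduces.
- After 20% loss (54 and 27): 0.924, or 0.918 with t. The plan's claim of more than 90% also reproduces.

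**2. How many patients were halted.** The documents do not say. Assuming that the planned accrual held (section 2: 102 patients over 34 months, so 3 per month) with 24 weeks of treatment:

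- 3 × 24/4.345 = 16.6 patients on treatment, 16% of 102.

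**3. What LOCF does to the primary contrast.** Assume that the 16.6 are spread evenly over 24 weeks, split 2:1, with no test after the halt and no other loss.

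- Halted before week 6: 16.6 × 6/24 = 4.1, omitted for lack of any follow-up test.
- Halted in weeks 6–12: 4.1, week-6 value carried forward.
- Halted in weeks 12–24: 8.3, week-12 value carried forward.
- Analysed: 102 − 4.1 = 97.9.

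The share of the 24-week effect present in an early value is unknown, so two cases are shown beside exclusion (noncentral t):

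| Case | Mean effect | Power, SD 2.0 | Power, SD 1.7 |
|---|---|---|---|
| Week 6 carries half, week 12 carries all | 1.6 × (1 − 4.14 × 0.5/97.86) = 1.57 | 0.951 | 0.989 |
| Both carry half | 1.6 × (1 − 12.43 × 0.5/97.86) = 1.50 | 0.933 | 0.983 |
| All halted patients excluded (85.4 left) | 1.60 | 0.931 | 0.982 |

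On these assumptions LOCF costs no more power than leaving the patients out.

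**4. What unadjudicated time does to event rates.** This is an illustration with the pilot's 6-month readmission rates (section 4: 30% placebo, 5% anakinra for 12 weeks). Assume a constant hazard, a halted fraction h, and a halt at fraction f of follow-up. If the remaining time were counted as event-free:

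- Apparent rate = (1 − h)p + h[1 − (1 − p)^f].
- With 17 halted (h = 0.167) and f = 0.25, placebo: 0.833 × 0.30 + 0.167 × 0.085 = 0.264.
- Over f = 0.25 to 0.50 with 17 halted: 26.4–27.7% versus 4.4–4.6%. The risk difference falls from 25 points to 22.0–23.1.
- With 12 halted the difference is 22.9–23.7 points; with 30 halted, 19.8–21.7.
- The risk ratio stays near 0.17 throughout. Both arms shrink in proportion.

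**5. Which rule governs.** A halted patient with a week-6 test and no week-24 test is imputed under section 11.3.2, but would be dropped under a literal complete-case reading of section 11.3.3. The plan therefore permits at least two primary analyses for the same patient.

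**The case against.** A reader might infer that the plan counts halted patients as event-free and as treated. The documents do not say so. Kaplan-Meier estimation can censor at the adjudication cut-off, although no date is written. Section 10.2 excludes patients whose clinical status cannot be established and brings them back in a sensitivity analysis over all outcomes. Analysis as randomized keeps a patient in the assigned arm and does not assert 24 weeks on drug. All of this stands, and it limits the event problem to the fixed-time rates and the day counts.

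Unadjudicated also does not mean unrecorded. Section 5.2 has hospitalizations recorded at each visit, and section 10.2 continues this from the medical record after withdrawal. That weakens the case on hospitalization-free days. It does not settle it, because the amendment describes the follow-up only in terms of research-related adverse events.

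LOCF does not reach every halted patient: those never tested are omitted, and those tested later are not imputed. The multiple imputation check is some protection. Clinical outcomes are exploratory, and section 11.1 says that readmission is not powered.

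A larger power loss is also tempting. Giving all 16.6 patients no effect yields 1.6 × (1 − 16.6/102) = 1.34 and power 0.885 at SD 2.0, or 0.80 with 20% loss as well. That does not measure LOCF, which carries forward on-treatment values. It would fit only if patients were tested late and had lost the whole effect.

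Section 10.2 does not close the gap. Its treatment-withdrawal rule is for permanent stops and its exclusion rule for patients lost to follow-up; halted patients were told to interrupt and were still followed.

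**Conclusion.** The point holds as a gap in the rules with a definite consequence if the text is followed. The 6-month event summaries cover time without adjudication, so adjudicated rates can be understated in both arms. A 6- or 12-week value can also become the 24-week primary endpoint, for a stop that the stated reason for LOCF does not fit.

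The numerical effect is modest under the assumed 17 halted patients: power of about 0.93–0.95 at SD 2.0, and an illustrative risk difference about 2 to 3 points smaller. It grows with the number halted, which only the sponsor knows. No bias toward either arm is shown. The stronger worry is that the treatment of perhaps one patient in six is open, with LOCF and complete case both in the text. It should be settled before unblinding. The amendment's suspension of adjudication also lacks an end date; read literally it covers patients enrolled after resumption, which cannot stand beside section 9.2.

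**What to change.** Add a short paragraph to sections 9.2, 10.2 and 11.3, before unblinding, for patients on study on 17 March 2020:

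- **Time to event:** censor adjudicated analyses at that date.
- **Fixed-time rates and hospitalization-free days:** include only patients whose 1-, 3- or 6-month window had closed by then, decided by enrollment date and not by whether an event occurred. Alternatively, use a rate per day of adjudicated follow-up.
- **Scope:** state that the suspension of adjudication covers these patients only, not those enrolled after resumption.
- **Peak VO₂:** leave tests missed because of the halt as missing in the repeated-measures model that the plan already names, instead of LOCF. Keep any test done after the halt in the intention-to-treat analysis. Setting observed values to missing would change the question being asked, so it belongs in a sensitivity analysis.
- **Sensitivity:** repeat the primary analysis without the halted patients, or without their post-halt values, and report how many there were.
- **Consistency:** reconcile LOCF in section 11.3.2 with complete case in section 11.3.3.

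The cost is the drafting, fewer follow-up days, and slightly wider intervals. The model-based approach assumes that visits missed through the halt are missing for reasons unrelated to outcome, which is plausible for a calendar-date stop.

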Appendix: DSMB Charter**1) KEY PERSONNEL**

Please refer to the IRB Roster and Delegation Log for a complete personnel list

Name	Role	Institution/ Division
[name]/PhD	Medical Responsible PI	VCU, Cardiology
[name] [name]	Study Operation PI	VCU, School of Pharmacy
[name]	Clinical Trial Operations	VCU, Cardiology
[name]	CPX Core Lab	University of Illinois, Chicago
[name]	Investigational Pharmacy	VCU, School of Pharmacy
[name]	Biostatistician	VCU, Biostatistics
[name]	DSMB Chair	University of Florida, Cardiology
[name]	DMSB member	VCU, Infectious disease
[name]	DSMB member	Virginia Cardiovascular Specialists
[name]	DSMB member	VCU, Immunology
[name]	DSMB member	VCU, Biostatistics, CCTR
[name]	DSMB liaison	VCU, Pauley Heart Center

Abbreviations: DSMB=Data Safety Monitoring Board

2) PROTOCOL SUMMARY

Title: Interleukin-1 Blockade in Recently Decompensated Heart Failure

Population: 102 patients (age >21 years) with a clinical diagnosis of systolic heart failure, and recent (within 2 weeks of discharge) hospitalization for heart failure

Site(s): Virginia Commonwealth University, Richmond, VA

Study Duration: 40 months

Description: Phase II clinical trial of Anakinra (or Placebo) (2:1 allocation) for the treatment of patients with recently decompensated systolic (LVEF≤40%) heart failure and increased systemic inflammation (CRP>2 mg/L)

Objectives: To determine the effects of Anakinra (or Placebo) on peak of aerobic exercise capacity (peak VO₂) measured with a cardiopulmonary test after 24 weeks

[figure not shown]
Study Design: Single-center, randomized, double-blinded, placebo-controlled clinical trial with allocation to Anakinra 100 mg daily or placebo in 2:1 ratio for 24 weeks

Estimated Time to Complete Enrollment: 36 months

Estimated Time to:

- First patient in:** 6-12 months from funding
- Last patient in:** 34 months from first patient enrolled
- Last patient out:** 40 months from first patient enrolled

3) SCHEMATIC OF STUDY DESIGN

4) DESCRIPTION

The **REDHART2** (*RE*cently *D*ecompensated *H*eart failure *A*nakinra *R*esponse *T*rial 2) study is a phase II clinical trial of anakinra or placebo to improve aerobic exercise capacity in patients with recently decompensated systolic heart failure (HF).

The recently completed pilot REDHART study, supported by a R34 NHLBI pilot clinical trial grant randomly assigned 60 patients with recently decompensated systolic heart failure to one of 3 strategies: 1) short-term treatment with anakinra for 14 days; 2) longer-term treatment with anakinra for 12 weeks; 3) placebo for 12 weeks. An additional group of eligible patients who declined participation in the study was enrolled in an observational study to evaluate the rate of HF hospitalizations. Anakinra treatment for 12 weeks led to a significant improvement in peak aerobic exercise capacity (peak VO_2), whereas anakinra treatment for 2 weeks did not. No significant changes were seen in placebo. The hospital readmission rate at 6 months was 5% in anakinra 12-week treatment group, 30% in the placebo group, 32% in the anakinra 2-week group, and 35% in the observational group of eligible patients who were not randomized to treatment.

The REDHART2 study is designed to expand and confirm the beneficial effect of sustained anakinra treatment (24 weeks) on peak VO_2 , and to explore the potential effect size on hospital readmissions for HF.

The rationale of Interleukin-1 (IL-1) blockade with anakinra in heart failure stems from the evidence of a) reduced adverse cardiac remodeling and heart failure in animal models of

acute myocardial infarction (AMI); *b*) reduced incidence of heart failure in patients with ST-segment elevation AMI; *c*) enhanced IL-1 activity in patients with heart failure, *d*) quenching of the acute inflammatory response in patients with acute decompensated heart failure, *e*) direct cardiodepressant effects of IL-1 in animal models, *f*) improved exercise capacity in pilot studies including patients with stable systolic heart failure, stable diastolic heart failure, and, recently decompensated systolic heart failure in the pilot REDHART study.

5) OBJECTIVES

The Objective of REDHART2 is to study the effects of IL-1 blockade with anakinra on parameters of aerobic exercise capacity (peak VO₂) at cardiopulmonary exercise test (CPX) after 24 weeks of active treatment, as well as the effects of anakinra on inflammatory biomarkers, structural and functional echocardiographic data, and non-invasive hemodynamics.

